In the present study, we will extend our previous findings and determine whether individuals with this phenotype also experience less positive effects from two other rewards: feelings of well-being from a single oral dose of d-amphetamine and preference for sweet solutions. This would suggest a mild dysfunction of the reward circuits in BPP individuals, possibly related to mesolimbic dopamine function.

**Study Aim: To compare the rewarding effects of d-amphetamine (10 and 20 mg) and sweet tastes in young adults with low and high bipolar phenotypes.** The rewarding effects of d-amphetamine in young adults will be measured using subjective self-report measures of euphoria and arousal. We will also obtain psychophysiological measures to provide an objective index of positive emotional responses. Based on our previous findings suggesting individuals with BPP display damped subjective responses to alcohol, we hypothesize that individuals

with BPP, compared to matched controls without these symptoms, will be hypo-reactive to both amphetamine reward and sweet taste reward.

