**Design & procedure:** Following orientation, participants will complete three 4-hour drug study visits and a final 1-hour visit. The 4-hour sessions will be conducted between 9am and 1pm separated by at least 48 hours in a double-blind, placebo-controlled, cross-over, within-subjects design. During these visits, they will consume capsules containing 10 or 20 mg d-amphetamine or placebo, double-blind in counterbalanced order. Women not using oral contraceptives will only be tested during the follicular phase (White et al., 2002).

Upon arrival at the laboratory, participants will provide BrAL and compliant urine tests for recent drug or alcohol use, and pregnancy (in females). Participants will then complete baseline questionnaires (DEQ, POMS, and the ARCI) and psychophysiological measurements. Participants will be given a snack (granola bar) to standardize food consumption, and then ingest a capsule containing placebo, 10mg or 20 mg d-amphetamine under double-blind conditions. The order will be randomized across subjects via Latin square design. Participants will complete the DEQ, POMS, and the ARCI scales at 30, 60, 90, 120, 150, 180, 210 and 240min time-points; HR will be taken at the same time. At 1pm, participants will complete a final set of questionnaires to collect their final state and subjective responses before being discharged to go home.

**The Sweet Taste Test:** On the final 1-hour study visit, participants will complete the sweet taste test and then the study will be explained. After BrAL and drug compliance tests, participants will complete the validated sweet taste test (Weafer et al., 2014). In this test, participants rate the sweetness intensity and liking of Kool-aid solutions of various sucrose concentrations.

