Participants will rate five concentrations equivalent to the molar sucrose concentrations typically used in sweet taste liking procedures (i.e. 0.05, 0.10, 0.21, 0.42 and 0.83M). The test will consist of five blocks, in which each of the five solutions will be presented in random order (i.e. a total of 25 taste trials). On each presentation, participants will receive a 2ml serving of solution in a small opaque cup, instructed to swish the solution for 5s and then spit it out. They rate the sweetness of the taste (from 'Not sweet at all' to 'Extremely sweet') and their liking of the taste (from 'Disliked very much' to 'Liked very much') on two 100-mm visual analog scales. Between trials, subjects will rinse and spit a small amount of water. Sweetness and liking ratings will be calculated by averaging ratings for each solution across the five presentations.

**Data analysis and interpretation:** First we will ensure that the BPP and HC groups are matched for demographic variables, and covariates will be identified if needed. Primary outcome measures will be the stimulant (A scale) and euphoria (MBG) subscales of the ARCI (Haertzen, 1966) and the Friendliness and Elation subscales of the POMs (McNair et al., 1971). These measures will be tested using GLMs with predictors of group (BPPs vs HCs), gender, treatment (placebo, 10mg and 20mg amphetamine) and time (0, 30, 60, 90, 120 and 150 and 180min). Sweet 'liking' responses will be tested using a GLM with the predictors of group, gender and concentration (i.e. 0.05, 0.10, 0.21, 0.42 and 0.83M). Participants will be classified as sweet-likers if their liking ratings were greatest for the highest concentration solution (0.83 M); all other participants will be classified as sweet-dislikers (Weafer et al., 2014).  $\chi^2$ -tests will test the supplementary prediction that there are more sweet-likers in the BPP group than in the HC groups.

**Sample size:** Estimations of sample/group size have been derived from our previous demonstration of blunted subjective response to alcohol in BPP compared to HC males (Yip et al., 2012). In that study, the effect sizes ( $f^2$ ) for the two DEQ sub-scales of 'Feel high' and 'Feel effects' was 0.73 and 0.60, respectively. Taking the midpoint of these 2 values as our anticipated effect size (0.67), N=48 subjects would provide over 81% power (with  $\alpha = .05$ ) to detect treatment differences between BPP individuals and HC individuals.

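### Four unranked primary outcomes serve one amphetamine hypothesis, with no multiplicity or success rule and no statement of which model term decides

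*Combined protocol and SAP*

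**What the plan says.** The Data analysis and interpretation paragraph opens its outcome list with "Primary outcome measures will be the stimulant (A scale) and euphoria (MBG) subscales of the ARCI" and completes it with "the Friendliness and Elation subscales of the POMs". The four scales are given no order. The next sentence gives the model: "These measures will be tested using GLMs with predictors of group (BPPs vs HCs), gender, treatment (placebo, 10mg and 20mg amphetamine) and time", with seven time points from 0 to 180 min. It lists predictors but does not say which main effect, interaction or contrast answers the question.

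The hypothesis, under Study Aim, is directional: participants with the bipolar phenotype "will be hypo-reactive to both amphetamine reward and sweet taste reward". The Sample size paragraph gives alpha as .05, undivided and without sidedness, and describes its power as power "to detect treatment differences between BPP individuals and HC individuals". Together these imply a group by treatment test, but neither passage says so.

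Sweet liking is handled separately: "responses will be tested using a GLM with the predictors of group, gender and concentration". It is not on the primary list.

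**The concern.** Four scales are offered as evidence for one claim, and the plan does not say what pattern of results would establish it. One significant scale of four, a majority, or all four could each be reported as confirming blunted amphetamine response. If one is enough, the error rate for the claim exceeds that of a single .05 test unless the four test statistics are perfectly correlated. Because the deciding term is also unnamed, a reader cannot tell a planned result from one chosen among several model terms. A rule written before analysis settles both points; the same rule written afterwards does not.

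**Working it through.** **The plan's own figure.** The documents state no family-wise error rate. The related figure is power of over 81% with N = 48, alpha .05 and an effect size of 0.67, labelled f² (midpoint of 0.73 and 0.60: 1.33 / 2 = 0.665). I take 24 per group, one value per participant and a two-sided t test, so the noncentrality is d × √(24/2) and the critical value is 2.013 on 46 df.

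- 0.67 read as d: noncentrality 2.32, power 62%.
- 0.67 read as d², so d = √0.67 = 0.82: noncentrality 2.84, power 79% (81% by the normal approximation).
- 0.67 read as f², so d = 2√0.67 = 1.64: noncentrality 5.67, power above 99.9%.

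Only the second, non-standard reading comes near 81%. That is a separate matter. It bears on this point only because the cost of a correction depends on the reading.

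**Error rate if any one of four counts.** Inputs: four outcomes (Data analysis paragraph) and alpha .05 (Sample size paragraph). Assumptions: two-sided tests, any one positive scale counts, and equal correlation ρ between the four test statistics.

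- Uncorrelated: 1 − 0.95⁴ = 18.5%.
- Upper bound under any dependence: 4 × .05 = 20%.
- Correlated: 1 − ∫ φ(z) [Φ((c − √ρ z)/√(1−ρ)) − Φ((−c − √ρ z)/√(1−ρ))]⁴ dz, with c = 1.960. For Holm, any rejection under the global null requires the smallest p-value to be below .05/4 = .0125, so c = 2.498.

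| ρ | Any of four at .05 | With Holm |
|---|---|---|
| 0 | 18.5% | 4.9% |
| .3 | 17.4% | 4.7% |
| .5 | 15.6% | 4.3% |
| .7 | 13.0% | 3.7% |
| .9 | 9.4% | 2.6% |

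Treatment has three levels, so group by treatment has two degrees of freedom. I checked that case by simulation (sum of two squared normals per scale, 400,000 draws, same ρ). Each uncorrected rate moved by less than half a percentage point, so the table serves for either form of test.

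**Power cost of Holm.** Two-group t tests, 24 per group, the same effect on all four scales, power for at least one significant scale, at ρ = .3/.5/.7/.9:

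- d = 0.67: uncorrected 93.2/89.0/83.3/74.3%, Holm 77.5/71.5/63.8/53.1%; loss 15.7/17.5/19.5/21.2 points.
- d = 0.82: uncorrected 98.5/96.5/93.6/88.2%, Holm 92.1/87.3/81.6/72.5%.
- d = 1.64: essentially 100% both ways.

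A single .05 test has 62%, 79% and over 99.9% on the same three readings. For one particular scale at Holm's strictest step (.0125), power is 40% if d = 0.67 and 60% if d = 0.82.

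**The case against.** Several parts of the case against stand.

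- **The test is not wholly unnamed.** The model class, predictors and time points are given, and the hypothesis and power sentence point to group by treatment. What is missing is the deciding term, not the model.
- **Zero correlation is the least plausible case.** The scales are two pairs, each from one questionnaire, completed by the same people in the same sessions. The 18.5% is the top of the equal-correlation range, so the range must be shown. Even at .9 the rate is nearly twice 5%.
- **Directional figures depend on an unspecified contrast.** A reader might infer that false support for blunting rises from 2.5% to 9.6% (1 − 0.975⁴). That needs a one-degree-of-freedom contrast per scale, which the plan does not specify. A two-degree-of-freedom term has no single direction.
- **Sweet liking is reasonably placed.** It shares the hypothesis sentence, which might suggest that its status is unclear. But it is off the primary list and has its own GLM, so it does not enlarge this family.
- **Time is partly settled.** Scales are collected later as well ("Participants will complete the DEQ, POMS, and the ARCI scales at 30, 60, 90, 120, 150, 180, 210 and 240min time-points"), but the analysis paragraph fixes 0 to 180 min. Reducing these points to one summary, or pooling doses, is a preference rather than a correction.

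The objection does not supply a rule: no passage ranks the outcomes, divides alpha or says how many must be positive.

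**Conclusion.** The concern holds as a gap in the decision rule. With any-one-of-four at two-sided .05, the chance of at least one false positive is about 9% to 18.5% for correlations from .9 down to 0 (15.6% at .5), against 5% for one test. This rests on the any-one reading and on correlations that the documents do not give.

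A reader might infer that the trial has a planned error rate of 18.5%, or that the sponsor intends to claim success on one scale. The documents do not support either: they are silent, and a rule requiring all four would cause no inflation. A reader might also multiply further, since a full factorial has four terms containing group by treatment. But the plan does not say that every such term would be tested or would count. The matter should be corrected before analysis. In a small laboratory study it does not invalidate the design.

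**What to change.** Add a few sentences to the Data analysis paragraph:

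1. For each primary outcome, the deciding term is group by treatment over the 0 to 180 min points already in the model.
2. Either apply Holm across the four scales (smallest p-value against .0125, then .0167, .025 and .05), which holds the any-false-positive rate at 5% or less under any correlation, or name one of the four as the sole primary outcome at .05.
3. Label the other model terms and drug-response scales exploratory. Sweet liking keeps its own analysis outside this family.
4. A single directional contrast, or one summary per session, is optional. If used, fix it before analysis.

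No new data are needed. The cost of Holm is power relative to uncorrected any-of-four testing: about 16 to 21 points if 0.67 is d, negligible if it is f². Power for at least one scale remains broadly comparable to that of a single .05 test (53% to 78% against 62% on the d reading). Power for any one particular scale can be lower, which favours the sole-primary option if one scale matters most. Requiring all four scales is not advised: on the d reading its power is only 24% to 49% for correlations of .3 to .9.

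### The primary crossover model has no session (visit) term, so a visit trend in the tested score stays in the error of the group x treatment comparison; adding session is a cheap improvement in precision, of unknown and possibly nil size

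*Combined protocol and SAP*

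**What the plan says.** All places are in the combined protocol and SAP, under Method.

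- **Design & procedure.** Each subject attends three drug visits and one short final visit ("participants will complete three 4-hour drug study visits and a final 1-hour visit"). Placebo, 10 mg and 20 mg are given "double-blind in counterbalanced order", and "The order will be randomized across subjects via Latin square design". The text does not say whether the square is applied within the BPP and HC groups or over all 48 subjects. Questionnaires are also completed before the capsule at every drug visit: "Participants will then complete baseline questionnaires (DEQ, POMS, and the ARCI) and psychophysiological measurements".
- **Data analysis and interpretation.** For the four primary outcomes (ARCI A and MBG, POMS Friendliness and Elation): "These measures will be tested using GLMs with predictors of group (BPPs vs HCs), gender, treatment (placebo, 10mg and 20mg amphetamine) and time". The time factor is "time (0, 30, 60, 90, 120 and 150 and 180min", that is, minutes within a visit. Visit, session, period and sequence are not listed. Subject and interactions are not listed either.
- **Covariates.** The only opening for further terms is "First we will ensure that the BPP and HC groups are matched for demographic variables, and covariates will be identified if needed". It concerns demographic matching of the groups, not visit.
- **Sample size.** The power statement is "to detect treatment differences between BPP individuals and HC individuals". With the hypothesis under Study Aim, that the BPP group responds less, this implies a group x treatment test, but no contrast is named.

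**The concern.** A crossover that counterbalances order does so because responses may change from visit to visit through practice, familiarity or habituation. Here the outcomes are self-report mood and drug-effect scales repeated over three visits. Counterbalancing prevents such a change from favouring one dose on average, but does not take it out of the residual. Subjects who receive 20 mg at visit 1 and placebo at visit 3 carry the trend with one sign. Those with the reverse order carry it with the other. Without a session term, that spread counts as noise in each subject's drug response.

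The hypothesis rests on comparing drug response between two groups of 24, so avoidable noise matters. Visit order is already recorded and would remove it.

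**Working it through.** **The plan's own power figure.** The plan states over 81% power for N = 48 and an effect size of 0.67, labelled f². It does not reproduce from those inputs: 0.67 read as f² gives 99.98% (1 df), and read as a standardised mean difference with 24 per group it gives 62% two-sided. That is a separate matter, and nothing below uses the 81%.

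**Inputs.** From the documents: 48 subjects, split evenly (24 per group); three visits; three treatments; alpha 0.05. Assumed, because the documents give no value: a two-sided test; a 1-df group x (20 mg minus placebo) contrast; an effect of 0.826 SD of the difference, chosen to give 80% power with no trend; a linear trend of b per visit in the tested score.

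**Step 1: how order enters the difference.** Let D be the visit number of 20 mg minus that of placebo. With three cyclic orders D takes the values 2, -1, -1 (or the reverse signs), so its mean is 0 and its variance is (4 + 1 + 1)/3 = 2. With all six orders, D is ±1 in four and ±2 in two, so its variance is (4×1 + 2×4)/6 = 2. The mean is zero either way, so there is no expected bias.

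**Step 2: variance.** With b in units of the SD of the 20 mg minus placebo difference, the variance of the difference rises from 1 to 1 + 2b².

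**Step 3: power without session.** Noncentral t, 46 df, noncentrality 0.826 × √12 / √(1 + 2b²):

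| b per visit | Variance | Noncentrality | Power | Equivalent N (48/variance) |
|---|---|---|---|---|
| 0 | 1.000 | 2.861 | 80.0% | 48 |
| 0.1 | 1.020 | 2.833 | 79.2% | 47 |
| 0.25 | 1.125 | 2.698 | 75.2% | 43 |
| 0.5 | 1.500 | 2.336 | 62.8% | 32 |

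In units of the within-visit SD (SD of the difference divided by √2) the variance is 1 + b². Trends of 0.1, 0.25 and 0.5 then give 79.6%, 77.6% and 70.7%. The last row of the table is extreme: from visit 1 to visit 3 it shifts the score by 1.0 SD, more than the 0.83 SD effect sought.

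**Step 4: power with session.** Simulated change from time 0, order balanced only over all subjects, 6,000 runs, b = 0, 0.1, 0.25, 0.5:

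- without session: 80.5%, 80.0%, 76.5%, 62.8%;
- with session: 79.6%, 79.6%, 80.7%, 79.1%;
- type I error without session: 4.7% to 5.5%.

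A simpler two-treatment simulation gave about 78% with session at every trend, so the cost with no trend is about 1-2 points. In 12,000 runs with three orders, power without and with session was 79.8% and 79.9% at b = 0.1, and 79.0% and 79.9% at b = 0.15. Any net gain therefore starts at roughly 0.1-0.15 SD of the difference per visit.

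The 2-df group x treatment test with the same effect starts lower but behaves alike: 71.2%, 70.1%, 66.1%, 51.5% without session and 69.9%, 69.3%, 70.5%, 69.7% with it.

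**Step 5: order balanced within each group.** Type I error without session was 5.0%, 5.1%, 4.1% and 1.7% at the same four trends, and 5.0% to 5.3% with session. The error term then contains a trend that the balanced contrast does not, so the test is conservative.

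**Step 6: which session term does the work.** A session main effect is constant within a visit, so it cancels from any contrast between times in that visit. In a check on a seven-time model with a trend of 0.5 acting only after dosing, the mean 20 mg group x treatment x time coefficient was -0.500204 both without session and with a session main effect. It moved to -0.692317 only when session x time was added. The change score with session gave the same -0.692317.

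**The case against.** **The list may be a summary.** It names no subject term and no interaction, not even the group x treatment term that the hypothesis needs. A reader might infer that the investigators decided to leave session out; the documents do not show that. This stands, but the term still has to be written down, because nothing in the plan supplies it.

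**Not every visit trend costs precision.** A reader might infer that any change across visits ends up in the error. That goes too far. Time 0 is measured at every drug visit and is in the model, so a test on change from time 0 or on group x treatment x time is unaffected by a constant visit-level shift. Only drift in the within-visit response then matters. This stands in full.

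**No harm is shown.** No document gives a visit trend, and every size above is assumed. At 0.25 within-visit SD the loss is about 2 points, and with no trend the added term loses a little power. This also stands and limits the point to a suggestion. It does not remove it, since the change is cheap and uses data already held.

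**The illustration uses one contrast of several.** True: the plan names none. The 2-df test shows the same pattern from a lower starting power.

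**Adding session with only a subject intercept would be unsafe on all seven times.** Correct. Simulation of that model with no trend gave type I error of about 11-13%, 26% and 38% at assumed within-visit correlations of 0.1, 0.3 and 0.5, with or without session. This is a condition on the fix. It is not evidence about the plan's test, whose error structure is not stated.

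**Conclusion.** The point holds as a cheap improvement in precision. The design counterbalances visit order and the listed primary model does not use it, so a visit trend in the tested score would inflate the error of the group x treatment comparison.

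A reader might infer that the crossover comparison is biased or its type I error inflated. The documents do not support that. Order is randomised, the expected bias is zero, and in simulation type I error stayed near 5% with order balanced overall and fell below it with order balanced within group.

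The size cannot be taken from the documents and may be nil. Under the assumed linear trends, the loss runs from about 1 point (0.1 SD of the difference per visit) to 5 points (0.25) and 17 points (0.5, an extreme case). These figures rest on a 1-df contrast set at 80% power, equal groups of 24 and complete data.

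**What to change.** 1. For each of the four primary outcomes, analyse one score per visit (for example the post-dose mean, or mean change from time 0). Include group, gender, treatment, group x treatment and session (1, 2, 3) as a categorical fixed effect, with subject as the repeated or random unit. State which group x treatment contrast tests the hypothesis.
2. If all seven times are kept in one model, include a subject-by-visit error term as well as subject. If the tested effect is group x treatment x time, add session x time too, since session alone recovers nothing there.
3. State whether order is balanced within BPP and HC. If it is, keep the session term, because omitting it makes the test conservative.

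**Cost.** Visit number follows from the visit dates, so no new data are needed, and the term can be added before unblinding even if enrolment is complete. The per-visit version uses 2 df and about 1-2 points of power if there is no trend, with no net gain below roughly 0.1-0.15 SD of the difference per visit. The seven-time version with session x time uses 2 + 2×6 = 14 df; its effect on power was not computed.

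### The primary GLM counts the pre-dose rating as a response level and does not adjust for it, which costs precision if group × treatment averaged over time is the deciding test

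*Combined protocol and SAP*

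**What the plan says.** Under Design & procedure, the study is a "double-blind, placebo-controlled, cross-over, within-subjects design" with three drug visits. At each visit, "Participants will then complete baseline questionnaires (DEQ, POMS, and the ARCI) and psychophysiological measurements". A snack follows, and participants are "and then ingest a capsule containing placebo, 10mg or 20 mg d-amphetamine under double-blind conditions" only after that, as the last step (the quoted clause begins with the word for this sequence). Post-dose ratings start at 30 min.

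Under Data analysis and interpretation, "Primary outcome measures will be the stimulant (A scale) and euphoria (MBG) subscales of the ARCI", together with the POMS Friendliness and Elation subscales. "These measures will be tested using GLMs with predictors of group (BPPs vs HCs), gender, treatment" (placebo, 10 mg, 20 mg) "and time (0, 30, 60, 90, 120 and 150 and 180min"). No interaction is named. The only text on covariates concerns whether the groups are "matched for demographic variables, and covariates will be identified if needed".

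The Study Aim predicts that the BPP group "will be hypo-reactive to both amphetamine reward and sweet taste reward". The Sample size paragraph likewise speaks of treatment differences between the two groups, without naming a model term.

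**The concern.** A rating taken before the capsule cannot carry a drug effect. It can do two useful things: serve as a reference for the later ratings, or explain some of their variance. A group × treatment term averaged over all seven levels does neither. It adds a level with zero expected effect to the average and leaves unused the information that the pre-dose score holds about that session.

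At stake is precision in a trial of 48 people, where the comparison of interest is an interaction between a between-person factor and a within-person factor. The baselines are already being collected at every visit, so the lost precision could be recovered at almost no cost.

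**Working it through.** The plan gives no figure on this point to reproduce, and it gives no correlation or SD for these ratings.

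**Inputs from the document.** Seven time levels, 0 to 180 min, of which six are post-dose. Three treatments. 48 participants, taken as 24 per group from the even distribution planned. That 0 min is the pre-dose rating is inferred from the visit schedule; no other reading fits it.

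**Assumptions.** No drug effect at 0 min. Residual variance 1 within a session after participant effects are removed. Within-session correlation r from 0 to 0.7, either equal for all pairs of ratings (compound symmetry, CS) or falling with separation as r^|i−j| (AR(1)).

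**Step 1: dilution.** Let m be the mean group × treatment contrast over 30-180 min. Averaged over seven levels it becomes (0 + 6m)/7 = 6m/7, or 85.7% of m. This needs no correlation.

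**Step 2: standardised signal per unit of m, under CS.**
- Seven-level average: (6/7)/√((1+6r)/7)
- 0 min removed: 1/√((1+5r)/6)
- 0 min removed and used as covariate: 1/√((1+5r)/6 − r²)

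Example at r = 0.5. The variances are 4/7 = 0.571, 3.5/6 = 0.583, and 0.583 − 0.25 = 0.333. The signals are 0.857/√0.571 = 1.134, 1/√0.583 = 1.309, and 1/√0.333 = 1.732. The loss from keeping 0 min is 1 − 1.134/1.309 = 13%. Relative efficiency is the squared ratio: (1.309/1.134)² = 1.33 for removal, then (1.732/1.309)² = 1.75 for the covariate, and 1.33 × 1.75 = 2.33 for both.

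The same calculation for the other cases, with the AR(1) matrix substituted where shown:

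| Structure | r | Standardised loss | Removing 0 min | Covariate, further factor | Both |
|---|---|---|---|---|---|
| CS | 0 | 7% | 1.17 | 1.00 | 1.17 |
| CS | 0.2 | 12% | 1.28 | 1.14 | 1.46 |
| CS | 0.5 | 13% | 1.33 | 1.75 | 2.33 |
| CS | 0.7 | 14% | 1.35 | 2.88 | 3.89 |
| AR(1) | 0.2 | 8% | 1.18 | 1.01 | 1.19 |
| AR(1) | 0.5 | 9% | 1.21 | 1.07 | 1.30 |
| AR(1) | 0.7 | 11% | 1.25 | 1.26 | 1.58 |

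The gain from removal is similar under both structures. The gain from the covariate depends heavily on the structure.

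**Step 3: the three-way term.** Group × treatment × time has 1 × 2 × 6 = 12 numerator df, against 1 × 2 = 2 for group × treatment. Here 0 min acts as the reference, so there is no dilution. Simulated power, with half the effect at 10 mg and assumed 20 mg effects of 0.95 (1.0 in the CS 0.7 row), was as follows. The post-dose shapes are 0.25, 0.75, 1, 1, 1, 1 (plateau) and 0.1, 0.4, 0.8, 1, 1, 0.8 (peaked). The three-way F is Greenhouse-Geisser corrected.

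| Scenario | Seven-level average | Baseline-adjusted, 30-180 min | Three-way |
|---|---|---|---|
| CS 0.2, plateau | 0.75 | 0.89 | 0.30 |
| CS 0.5, plateau | 0.47 | 0.85 | 0.50 |
| CS 0.5, peaked | 0.34 | 0.68 | 0.49 |
| CS 0.7, peaked | 0.29 | 0.82 | 0.83 |
| AR(1) 0.5, peaked | 0.51 | 0.63 | 0.27 |

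The order of the first and third columns changes between scenarios, so neither of those two tests is generally better. The adjusted test beats the seven-level average throughout, and the three-way test catches up with it only at high r with a peaked effect.

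**The case against.** The strongest reply is that baseline as a time level is a standard repeated-measures layout. That stands. A reader might infer that the model is wrong or biased, and the documents do not support this. Under group × treatment × time the 0 min rating does its proper job, and the cost arises only if a time-averaged term decides.

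A second reply is that the deciding term is already implied, because the aim and the power sentence both describe a group difference in drug response. This largely stands too. It is the reason for taking the time-averaged group × treatment reading seriously. The two readings worked through above are not the only ones: a linear dose trend or a single-dose contrast would also fit the text.

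A third reply is that the large efficiencies depend on compound symmetry, under which the pre-dose score predicts 180 min as well as 30 min. That is correct. A reader might take 2.33 or 3.89 as the demonstrated loss, but under AR(1) the covariate alone adds 1%, 7% and 26% at r of 0.2, 0.5 and 0.7, and the documents give neither r nor its structure.

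Finally, the covariate clause does not rule out a baseline covariate. True, but it is conditional and tied to demographic matching, so it does not pre-specify one.

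**Conclusion.** The point holds as a loss of precision under the time-averaged group × treatment reading. The 6/7 factor follows from the listed time levels, given no drug effect at 0 min. The 7% to 14% standardised loss also rests on the assumed r of 0 to 0.7. Removing 0 min gains 17% to 35% in efficiency under CS, or 17% to 25% under AR(1). The further gain from adjustment runs from nothing (r = 0) to large (CS, high r) and cannot be fixed from the documents.

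Under the three-way reading nothing is diluted. The test then spreads over 12 df and asks whether the group difference changes over time, rather than whether the BPP group responds less overall.

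A reader might also infer inflated type I error from a choice between candidate tests. That is not claimed: the plan describes no such choice, and the averaged tests rejected in 4.4% to 5.2% of simulated null trials. The change is worth making, but its absence does not invalidate the analysis.

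**What to change.** For each primary outcome, name group × treatment over the post-dose ratings in the plan's own window (30-180 min) as the primary test, and keep the gender term. Take 0 min out of the response and enter each session's pre-dose score as a covariate, split into the participant's mean over the three sessions and the session's deviation from that mean. The split lets the treatment contrast use within-participant variation, so that a difference between BPP and control participants in usual mood does not enter it. Keeping 0 min as a response, with pre-dose means constrained equal across treatments within group, serves the same purpose. Retain group × treatment × time as secondary.

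The cost is analysis wording and one or two degrees of freedom. Without gender or period terms, group × treatment has 144 − 48 − 2 − 2 = 92 residual df, so this is minor. If r is near 0 the covariate adds nothing and only the gain from removing 0 min remains. If r is high and the effect sharply peaked, the three-way test may do as well as the proposed primary or slightly better.
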